8.10. Follow-up Post Completion of Vaccinations

At Study Months 13 and 18, the subject will visit the study center and have the following procedures performed:

- Pre-donation screening examination (see [Table 4](#)).
- Medication review
- Review of birth control methods for women of childbearing potential and obtain verbal report of pregnancy status
- AEs and diary card review
- Perform plasmapheresis and collect plasma sample for anti-tetanus and anti-diphtheria antibody titer tests
- Query subject about AEs before leaving the center

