13.5. Compensation for Participation

Subjects will be compensated for travel expenses and for time contributed to this research study in the form of cash. Subjects will receive the normal payments for plasma donations and the initial Tdap vaccination and will receive additional compensation for study participation. The payment schedule is shown in [Table 6](#).

Table 6: Subject Payment Schedule

Extra Study Specific Procedure	Payment for each Procedure	Total Number of Procedures over 18 months	Total Extra Payment for Study Participation
Additional compensation (regular plasma donation)	\$5.00	150	\$750.00
Additional compensation (vaccinations)	\$10.00	4 (the first vaccination is a standard procedure the rest are additional protocol specified procedures)	\$40.00
Total			\$790.00

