9.5. Analysis of Safety Endpoints

Treatment emergence will be evaluated for all AEs. Treatment-emergent adverse events (TEAEs) are those that occur on or after the same date and time of first dose of study drug. TEAEs will be coded using the most recent version of the Medical Dictionary of Regulatory Affairs (MedDRA) by assigning a preferred term and will be grouped by system, organ, and class (SOC) designation. AEs occurring after each vaccination up to the time of the next vaccination and separately over the whole study period will be summarized. Separate tables will be provided for solicited AEs reported within the 3 day period after each vaccination.

Each AE will be counted once only by preferred term for a given study subject within each post vaccination time period prior to the next vaccination or up to the 6-month follow-up visit after the last vaccination. If the same AE occurred on multiple occasions, the highest severity and relationship to investigational product will be assumed within each time period.

The summary tables will include an overall summary of number and percentage of subjects reporting each TEAE, summary by relationship, summary by severity will be presented by each vaccination period and overall.

Listings of each individual AE including start date, stop date, severity, relationship, duration, outcome, and actions taken will be provided.

Reactogenicity is defined as the total count of a set of solicited AEs that are expected after a vaccine. A regression analysis will be performed with reactogenicity as the dependent variable and anti-diphtheria titers as the independent variable to determine if there is an association. Anti-diphtheria titer is not expected to be normally distributed and will be natural log transformed. Null Hypothesis of no association between reactogenicity and anti-diphtheria titers will be tested on

Slope obtained using simple linear regression analysis at alpha=0.01 using two-sided tests. The null hypothesis states that the slope is equal to zero, and the alternative hypothesis states that the slope is not equal to zero. No adjustment for covariates will be made. The following SAS procedure PROC REG may be used.

```
Proc reg data=data;
Model reactogenicity =log(anti_diphtheria_titers);
Run;
```

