Characteristic	ITT N=xx	Per-protocol N=xx
Gender		
Male	xx (x.x%)	xx (x.x%)
Female	xx (x.x%)	xx (x.x%)
Age (years at date of consent)		
Mean (SD)	xx.x (x.xx)	xx.x (x.xx)
Median	xx.x	xx.x
Min-Max	(xx – xx)	(xx – xx)
Maximum		
Race		
Black or African American	xx (x.x%)	xx (x.x%)
American Indian or Alaskan Native	xx (x.x%)	xx (x.x%)
Asian	xx (x.x%)	xx (x.x%)
Native Hawaiian or Other Pacific Islander	xx (x.x%)	xx (x.x%)
White	xx (x.x%)	xx (x.x%)
Other/Unknown	xx (x.x%)	xx (x.x%)
	xx (x.x%)	xx (x.x%)
Ethnicity		
Hispanic or Latino	xx (x.x%)	xx (x.x%)
Not Hispanic or Latino	xx (x.x%)	xx (x.x%)
Not Reported	xx (x.x%)	xx (x.x%)

<Program Name: Time and Date>

Table 4: Summary of Protocol and Treatment Compliance

	ITT N=xx
Protocol compliance rate^a	
Month 0	xx.x%
Month 3	xx.x%
Month 6	xx.x%
Month 9	xx.x%
Month 12	xx.x%
Number of Tdap vaccinations	
Mean (SD)	xx.x (x.xx)
Median	xx.x
Min-Max	(xx – xx)
Total Tdap vaccination dose (mL)	
Mean (SD)	xx.x (x.xx)
Median	xx.x
Min-Max	(xx – xx)

^aProtocol compliance is presented as percentages of subjects attending each scheduled treatment visit.

<Program Name: Time and Date>

Table 5: Summary of Plasmapheresis Check by Visit - ITT Population

Visit		n (%)
Screening	Eligible for Plasmapheresis	
	Yes	xx.x (x.xx)
	No, Temporary	xx.x (x.xx)
	No, Permanent	xx.x (x.xx)
	If "No, Temporary", Inclusion Criteria not Met	
	Temperature: 97.0 - 99.5 °F	xx.x (x.xx)
	Blood Pressure: 90 - 180/50 - 90 mmHg	xx.x (x.xx)
	Pulse: 50 - 100 beats/min	xx.x (x.xx)
	(List all criteria not met)	
(Repeat for all visits)		

<Program Name: Time and Date>

Table 6: Summary of Treatment-emergent Adverse Events - ITT Population

	Vaccination Number					Overall N=xx
	1 N=xx	2 N=xx	3 N=xx	4 N=xx	5 N=xx	
Number of AEs	xx	xx	xx	xx	xx	xx
Number of SAEs	xx	xx	xx	xx	xx	xx
Number of AEs related to study product	xx	xx	xx	xx	xx	xx
Number (%) of subjects with						
At least one AE	xx (x.x%)	xx (x.x%)	xx (x.x%)	xx (x.x%)	xx (x.x%)	xx (x.x%)
At least one SAE	xx (x.x%)	xx (x.x%)	xx (x.x%)	xx (x.x%)	xx (x.x%)	xx (x.x%)
At least one AE related to study product	xx (x.x%)	xx (x.x%)	xx (x.x%)	xx (x.x%)	xx (x.x%)	xx (x.x%)
Number of AEs by severity						
Mild	xx	xx	xx	xx	xx	xx
Moderate	xx	xx	xx	xx	xx	xx
Severe	xx	xx	xx	xx	xx	xx
Number of AEs by relationship to study product						
Unrelated	xx	xx	xx	xx	xx	xx
Unlikely	xx	xx	xx	xx	xx	xx
Possible	xx	xx	xx	xx	xx	xx
Probable	xx	xx	xx	xx	xx	xx
Definite						
Serious?						
Yes	xx	xx	xx	xx	xx	xx
No						

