Note: AEs occurring after each vaccination up to the time of the next vaccination is summarized.

<Program Name: Time and Date>

Table 7: Summary of Solicited Treatment-emergent Adverse Events - ITT Population

	Vaccination Number					Overall N=xx
	1 N=xx	2 N=xx	3 N=xx	4 N=xx	5 N=xx	
Number of Solicited TEAEs	xx	xx	xx	xx	xx	xx
Number of AEs related to study product	xx	xx	xx	xx	xx	xx
Number (%) of subjects with						
At least one solicited TEAE	xx (x.x%)	xx (x.x%)	xx (x.x%)	xx (x.x%)	xx (x.x%)	xx (x.x%)
At least one AE related to study product	xx (x.x%)	xx (x.x%)	xx (x.x%)	xx (x.x%)	xx (x.x%)	xx (x.x%)
Number of Solicited TEAEs by severity						
Mild	xx	xx	xx	xx	xx	xx
Moderate	xx	xx	xx	xx	xx	xx
Severe	xx	xx	xx	xx	xx	xx
Number of Solicited TEAEs by						
relationship to study product	xx	xx	xx	xx	xx	xx
Unrelated	xx	xx	xx	xx	xx	xx
Unlikely	xx	xx	xx	xx	xx	xx
Possible	xx	xx	xx	xx	xx	xx
Probable	xx	xx	xx	xx	xx	xx
Definite						

N = Number of Subjects

Note: Solicited AEs reported within the 3 day period after each vaccination is summarized.

<Program Name: Time and Date>

Table 8: Number (%) of Subjects with Treatment-emergent Adverse Events by System Organ Class and Preferred Term - ITT Population

System, Organ, Class/ Preferred Term	Vaccination Number					Overall N=xx n (%)
	1 N=xx n (%)	2 N=xx n (%)	3 N=xx n (%)	4 N=xx n (%)	5 N=xx n (%)	
SOC 1	xx (xx.x)					
Preferred Term 1	xx (xx.x)					
SOC 2	xx (xx.x)					
Preferred Term 2	xx (xx.x)					

Note: Subjects are counted only once within each system organ class and preferred term.

<Program Name: Time and Date>

Table 9: Number (%) of Subjects withSolicited Treatment-emergent Adverse Events by System Organ Class and Preferred Term - ITT Population

System, Organ, Class/ Preferred Term	Vaccination Number					Overall N=xx n (%)
	1 N=xx n (%)	2 N=xx n (%)	3 N=xx n (%)	4 N=xx n (%)	5 N=xx n (%)	
SOC 1	xx (xx.x)					
Preferred Term 1	xx (xx.x)					
SOC 2	xx (xx.x)					
Preferred Term 2	xx (xx.x)					

: Note: Solicited AEs reported within the 3 day period after each vaccination is summarized.

Subjects are counted only once within each system organ class and preferred term.

<Program Name: Time and Date>

Table 10: Summary of Subjects with Treatment-emergent Adverse Events by Severity and Relationship - ITT Population

System, Organ, Class\ Preferred Term	Number of Subjects (%) (N=xx)								
	Mild		Moderate		Severe		All Grades		Total
	R	NR	R	NR	R	NR	R	NR	R + NR
SOC									

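### Tables 6 and 8 count adverse events for about 3 months after doses 1-4 but 6 months after dose 5, so a flat background rate of unsolicited AEs and SAEs can look like a rise at the last dose

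*SAP*

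**What the plan says.** SAP 9.5 and protocol 12.2.3 use the same rule: an AE is counted once per subject and preferred term "within each post vaccination time period prior to the next vaccination or up to the 6-month follow-up visit after the last vaccination". Protocol 7.4 sets doses 3 months ± 1 week apart, and protocol 6.4 sets 6 months of follow-up after the last dose.

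In SAP Appendix A, the shell "Table 6: Summary of Treatment-emergent Adverse Events - ITT Population" has one column per vaccination plus Overall. It shows event counts, SAE counts and n (%) of subjects. Its note reads "AEs occurring after each vaccination up to the time of the next vaccination is summarized", which sets no end for dose 5 because no further dose follows. Table 8 uses the same columns for n (%) by system organ class and preferred term. Its note says only "Subjects are counted only once within each system organ class and preferred term".

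Solicited reactions are handled differently. SAP 9.5 states "Separate tables will be provided for solicited AEs reported within the 3 day period after each vaccination", and the note to Table 7 reads "Solicited AEs reported within the 3 day period after each vaccination is summarized"; Table 9 carries the same window. The SAP does not say whether solicited reactions also enter Tables 6 and 8. Inclusion is the more natural reading, since all TEAEs are summarised and the solicited tables come in addition.

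**The concern.** The primary objective is the safety of repeated dosing at shortened intervals, and there is no control arm. A reader will therefore look across the five vaccination columns for a rise with successive doses. Unsolicited AEs and SAEs are tabulated by dose only in Tables 6 and 8, and there the last column has about twice the observation time of the others. Events unrelated to the vaccine and arising at a steady rate would produce the pattern that a cumulative-dose problem would produce. A reader of the tables alone could not see why, because the notes do not disclose the longer window.

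Tables 7 and 9 (equal windows), Table 10 (no vaccination columns), and Tables 11 and 12 are not affected.

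**Working it through.** The plan gives no figure to reproduce for this point and no background rate for unsolicited AEs or SAEs. The incidences below are assumptions, shown as a range.

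**Windows.** Doses 1-4: 3 months, about 13 weeks, or 12 to 14 with the ± 1 week allowance. Dose 5: 6 months, about 26 weeks. Check: 4 × 3 + 6 = 18 months, the stated study period. Ratio: 26/13 = 2.0; range 26/14 = 1.86 to 26/12 = 2.17.

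**Proportion of subjects with a given event.** With constant rate and incidence p per 3 months, column 5 shows 1 − (1 − p)². This respects the once-per-period rule.

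| p, doses 1-4 | Column 5 | Ratio |
|---|---|---|
| 5% | 9.75% | 1.95 |
| 10% | 19% | 1.90 |
| 20% | 36% | 1.80 |
| 30% | 51% | 1.70 |

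For rare events the ratio approaches 2.

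**How often column 5 would stand out with no true change.** Take five independent binomial counts with 100 subjects per column. The table gives the probability that column 5 is strictly the highest.

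| p | Equal windows | 26 vs 13 weeks |
|---|---|---|
| 5% | 0.156 | 0.711 |
| 10% | 0.166 | 0.882 |
| 20% | 0.173 | 0.978 |
| 30% | 0.176 | 0.995 |

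For rare events such as SAEs, use Poisson counts with mean 0.5, 1 or 2 per 3 months. The probabilities are 0.253, 0.349 and 0.483, against 0.107, 0.122 and 0.139 with equal windows.

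**What reduces the effect.**
- Dropout: with 80 subjects followed after dose 5 and 100 before, the 2.0 ratio of expected counts becomes 2 × 0.8 = 1.6. The probabilities for counts of affected subjects become 0.49, 0.64, 0.79 and 0.84. Percentages change little, because the denominator falls too.
- Capture: protocol 8.10 states "At Study Months 13 and 18, the subject will visit the study center and have the following procedures performed", so routine visits are no longer monthly. If a fraction c of events in Months 13-18 is captured and Month 12-13 is complete, the effective window ratio is (1 + 5c)/3. This is 1.67 at c = 0.8 and 1.17 at c = 0.5. The probabilities over p = 5-30% then run 0.54-0.94 and 0.24-0.42.
- Solicited reactions, if included in the any-AE row of Table 6: take 65.7% injection-site pain (protocol 4.5) as an upper-end proxy and an independent background b of 5-30%. The row moves from 1 − 0.343(1 − b) to 1 − 0.343(1 − b)². That is 67.4% to 69.0% at b = 5% and 76.0% to 83.2% at b = 30%, ratios of 1.02 to 1.09. SAE rows and uncommon preferred terms are not diluted in this way.

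**The case against.** The strongest reply is that the plan already contains most of what a careful reader needs. Both documents state the longer window in the text. No test compares doses. Acute reactions have equal windows. Listings 8 and 11 carry vaccination dates and AE onset dates. Table 6 also shows, for each dose, the AEs judged related and a five-level relationship breakdown. Background events in Months 15-18 should fall mainly in the unrelated or unlikely rows, so the related rows are much less exposed to the longer window. All of this stands, and it keeps the point small. The safeguard is partial, however, because neither the SAE rows of Table 6 nor Table 8 is split by relationship.

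It can also be said that being strictly the highest of five is not a decision rule in either document, and that for SAEs column 5 would usually not be the strict maximum (25-48%). That is right. The probabilities only gauge how visible the artefact is.

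Three stronger readings are tempting, and the documents do not support them.
- A reader might infer that every dose 5 figure doubles. Once-per-term counting, dropout and incomplete capture all pull below 2, and the any-AE row may hardly move.
- A reader might infer that no study visit falls between dose 5 and Month 13. Protocol 8.8 plans a visit 1 to 3 days after each vaccination, Month 12 included, and the schedule gives Month 12 two visit numbers (18/19).
- A reader might infer an inflated false-positive rate. With no test across doses there is none.

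Finally, a one-line footnote might seem enough. It would disclose the imbalance but leave the reader unable to remove it from the summary tables.

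**Conclusion.** The point holds as a cheap improvement to the presentation of the primary safety endpoint. All-cause unsolicited AE and SAE figures in column 5 of Tables 6 and 8 rest on about twice the observation time of the other columns. At a flat rate this inflates rare events about 2-fold, and the proportion of subjects by 1.95 to 1.7 times at an assumed 5-30% per 3 months.

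The upper figures assume a constant rate, full capture to Month 18 and, for the count rows, the same number of subjects in each column. The documents give neither the background rate nor the capture, so the realised size is unknown. The difference in windows is certain. The harm is a misleading descriptive trend and nothing beyond that. Whatever is decided about the columns, the Table 6 note is incomplete against SAP 9.5 for dose 5 and needs correcting.

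**What to change.** In Tables 6 and 8, split the dose 5 period by AE onset date into two adjacent columns: 0-3 months after dose 5, and late follow-up (more than 3 months, to Month 18). Apply the once-per-period rule within each part and leave the Overall column unchanged.

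Correct the Table 6 note and give Table 8 the same one. It should state:
1. the two dose 5 windows;
2. whether solicited reactions are included;
3. how many AEs were placed by an imputed onset date, because SAP 10 sets a missing day to the first of the month;
4. that after the visit 1 to 3 days post-vaccination the remaining scheduled study visits are at Months 13 and 18, not monthly, so the 0-3 month column may read low and must be read beside the late column.

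Record the change in SAP section 12, which now declares no departures from the protocol, before database lock.

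**Cost.** One extra column in two shells, a longer note and a stated departure from the protocol 12.2.3 counting period. No new data are needed.

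**Downside.** Under incomplete capture the 0-3 month column covers an effective (1 + 2c)/3 of a normal window: 0.87 at c = 0.8 and 0.67 at c = 0.5. It is further from parity than the present column once c falls below 0.57 on the difference scale (5c − 2 = 2 − 2c) or 0.61 on the ratio scale ((1 + 5c)(1 + 2c) = 9). It should therefore never be shown alone. Capture may be better than the visit schedule suggests: the protocol 13.5 payment table, under "Total Number of Procedures over 18 months", budgets 150 donations, or 150/78 = 1.9 a week. The documents do not clearly say, however, that AEs are recorded at those donation visits.

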5.3. Baseline and Other Assessments

A complete medical history and demography (gender, age, race, and ethnicity) will be collected at the screening visit. Medications being taken by the subject in the 7-day period prior to the first vaccination through the completion of the study along with complete immunization history will be recorded and reported on an eCRF.

Vitals signs, full physical examinations and hematocrit and total protein determinations as part of the routine plasmapheresis will be assessed during pre-donation screening.

Infectious disease testing will be performed on all plasma samples collected from plasma donations and if a subject is positive for any of these infectious diseases, they will be taken off study. In addition, RPR (syphilis test) is performed every 4 months. If the subject is a first time donor, they must have two sequential plasma donations that are negative for the following infectious diseases to be eligible for plasmapheresis: Anti-HIV-1/2, HBsAg, Anti-HCV, SPE/RPR, Indirect Coombs, and PCR testing for HIV-1, HBV and HCV, HAV, and Parvovirus B19.

An eligibility checklist will be completed at screening. If the subject is not eligible for the study, a Reasons Not Eligible eCRF will be completed.

A dipstick urinalysis will be performed that tests for protein, blood, leukocyte esterase, nitrates, pH, specific gravity, ketones, bilirubin, and glucose. A blood sample will also be collected for a serum creatinine test. These tests will be performed to monitor for the possible development of immune complex-mediated glomerular disease.

Anti-diphtheria antibody levels will be measured at a central laboratory using the EUROIMMUN Anti-Diphtheria Toxoid ELISA (IgG). High anti-diphtheria titers will be assessed for an association with an increase in reactogenicity.

6. Hypotheses to be Tested

Hypothesis tests will be performed in order to determine if there is an association between reactogenicity and anti-diphtheria titers. Null Hypothesis of no association between reactogenicity and anti-diphtheria titers will be tested on Slope obtained using simple linear regression analysis at alpha=0.01 using two-sided tests.

7. Sample Size

One hundred subjects will be enrolled in this study.

8. Data Quality Assurance

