In addition, 2x2 tables will be created with presence or absence of moderate to severe reactogenicity versus high or not anti-diphtheria titers. Cut points of 75th percentile or 90th percentile of the anti-diphtheria titers will be used to define high level. The following SAS procedure PROC FREQ may be used.

```
Proc freq data=data;
Table reactogenicity*anti_diphtheria_titers/nopercent nocol;
Weight count;
Run;
```

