Preferred Term	xx (xx.x)	xx (xx.x)	xx (xx.x)	xx (xx.x)	xx (xx.x)	xx (xx.x)	xx (xx.x)	xx (xx.x)	xx (xx.x)

Note: Subjects are counted only once by preferred term at the highest severity grade and closest relationship to the investigational product.

R = Related to investigational product (possible, probable, definite). NR = Not related to investigational product (unrelated, unlikely).

Table 11: Contingency Table of Reactogenicity and Anti-diphtheria titers - ITT Population

Vaccination Number	Moderate to Severe Reactogenicity	Anti-diphtheria Titers		Total n (%)
		High = Yes n (%)	High = No n (%)	
1	Present	xx (xx.x)	xx (xx.x)	xx (xx.x)
	Absent	xx (xx.x)	xx (xx.x)	xx (xx.x)
	Total	xx (xx.x)	xx (xx.x)	xx (xx.x)
2	Present	xx (xx.x)	xx (xx.x)	xx (xx.x)
	Absent	xx (xx.x)	xx (xx.x)	xx (xx.x)
	Total	xx (xx.x)	xx (xx.x)	xx (xx.x)
3	Present	xx (xx.x)	xx (xx.x)	xx (xx.x)
	Absent	xx (xx.x)	xx (xx.x)	xx (xx.x)
	Total	xx (xx.x)	xx (xx.x)	xx (xx.x)
4	Present	xx (xx.x)	xx (xx.x)	xx (xx.x)
	Absent	xx (xx.x)	xx (xx.x)	xx (xx.x)
	Total	xx (xx.x)	xx (xx.x)	xx (xx.x)
5	Present	xx (xx.x)	xx (xx.x)	xx (xx.x)
	Absent	xx (xx.x)	xx (xx.x)	xx (xx.x)
	Total	xx (xx.x)	xx (xx.x)	xx (xx.x)
Overall	Present	xx (xx.x)	xx (xx.x)	
	Absent	xx (xx.x)	xx (xx.x)	
	Total	xx (xx.x)	xx (xx.x)	

Note: Reactogenicity is defined as the total count of a set of solicited AEs that are expected for up to 3 days after each vaccination. Cut points of 75th percentile of the anti-diphtheria titers is used to define high level.
 <Program Name: Time and Date>

Table 12: Summary of Serum Creatinine and Urinalysis Tests - ITT Population

Parameter (Unit)		Month 0	Month 3	Month 6	Month 9	Month 12
		n (%)				
Serum Creatinine	Low	xx (x.x)				
	High	xx (x.x)				
Specific Gravity	1.000	xx (x.x)				
	1.005	xx (x.x)				
	xx (x.x)				
pH	5	xx (x.x)				
	6	xx (x.x)				
	xx (x.x)				
Leucocytes	Negative	xx (x.x)				
	Trace	xx (x.x)				
	xx (x.x)				
Nitrite	Negative	xx (x.x)				
	Positive	xx (x.x)				
Protein (mg/dL)	Negative	xx (x.x)				
	Trace	xx (x.x)				
	xx (x.x)				
Glucose (mg/dL)	Normal	xx (x.x)				
	50	xx (x.x)				
	xx (x.x)				
Ketones	Negative	xx (x.x)				
	+/small	xx (x.x)				
	xx (x.x)				
Urobilinogen	Normal	xx (x.x)				
	1	xx (x.x)				
	xx (x.x)				
Bilirubin	Negative	xx (x.x)				
	+	xx (x.x)				
	xx (x.x)				
Blood/Hemoglobin (ery/uL)	Negative	xx (x.x)				
	Trace(blood)	xx (x.x)				
	xx (x.x)				

Table 13: Summary of Anti-tetanus Antibody Titers (IU/mL)

Visit	Statistics	ITT (N=xx)	Per-protocol (N=xx)

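### Reaction severity is related to anti-diphtheria titer only through percentile-cut 2x2 tables with no planned estimate or test; the regression that keeps the titer continuous ignores grade

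*SAP*

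**What the plan says.** SAP 9.5 plans two analyses of anti-diphtheria titer and reactogenicity; protocol 12.2.3 has the same pair.

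- **Regression.** The outcome is a count: "Reactogenicity is defined as the total count of a set of solicited AEs that are expected after a vaccine". The predictor stays continuous: "Anti-diphtheria titer is not expected to be normally distributed and will be natural log transformed". The test is on the "Slope obtained using simple linear regression analysis at alpha=0.01 using two-sided tests".
- **2x2 tables.** "2x2 tables will be created with presence or absence of moderate to severe reactogenicity versus high or not anti-diphtheria titers". The split is given as: "Cut points of 75th percentile or 90th percentile of the anti-diphtheria titers will be used to define high level". The shell of Table 11 (SAP Appendix A), laid out by vaccination and overall, has only one cut: "Cut points of 75th percentile of the anti-diphtheria titers is used to define high level".

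The sample PROC FREQ statement is "Table reactogenicity*anti_diphtheria_titers/nopercent nocol". It has no option for a chi-square test, exact test, odds ratio or confidence interval, and the Table 11 shell has no cell for any of these. SAP section 6 names only the regression slope for hypothesis testing.

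On size, SAP section 7 says only: "One hundred subjects will be enrolled in this study". Neither document gives a power figure or target effect for either analysis.

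**The concern.** Severity is part of the safety endpoint (protocol 9.2, SAP 3.3). Protocol 11.2.7 and SAP 5.3 also ask whether high anti-diphtheria titers go with greater reactogenicity. Yet the model with the better predictor has an outcome blind to grade, and the analysis with the graded outcome has a coarsened predictor. The documents give no clinical or laboratory reason for either percentile, and the ln-transformed titer is already in the dataset.

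Two smaller gaps compound this. Reactogenicity is defined only as a count, so it is not stated what makes it moderate to severe. Nor does the SAP say which visit's titer is paired with which vaccination.

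At stake is whether the report can say how strongly titer is related to worse reactions, and with what precision. As planned it would give cell counts and percentages only.

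**Working it through.** **1. Where titer meets severity.** Going through the SAP shells: Tables 6, 7 and 10 show severity without titer; Table 14 shows titer without severity; Figure 1 plots the count on titer. Only Table 11 has both.

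**2. Information kept by the cut.** There is no figure in the plan to reproduce. Assume ln titer is normal and the effect is linear in ln titer. A split with upper fraction p at normal quantile z keeps φ(z)²/[p(1−p)] of the information, the squared correlation between split and continuous titer.

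- 75th percentile: p = 0.25, z = 0.674, φ = 0.318; 0.318²/0.1875 = 0.54.
- 90th percentile: p = 0.10, z = 1.282, φ = 0.1755; 0.1755²/0.09 = 0.34.

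For this question 100 subjects then count as about 54 or 34. The high column holds 100 × 0.25 = 25 or 100 × 0.10 = 10 people. At an assumed 25% event rate with no titer effect, it would hold 6.25 or 2.5 expected events.

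**3. What that could mean if a test were run.** Assumed inputs: odds ratio (OR) 1.5 to 3.0 per SD of ln titer; rate of any moderate-to-severe reaction 16.2%, 25% or 35%. The low end is injection-site pain alone in protocol Table 2 (15.1% + 1.1% = 16.2%). Method: simulation of one vaccination, N = 100, one record per subject, 1,500 runs, Pearson test on the 2x2 table against the likelihood-ratio test from logistic regression on continuous ln titer. Power at a 25% event rate, two-sided alpha 0.01 / 0.05:

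| OR per SD | Rate above v below 75th | 2x2 at 75th | 2x2 at 90th | Continuous |
|---|---|---|---|---|
| 1.5 | 35% v 22% | 14% / 30% | 11% / 25% | 22% / 44% |
| 2.0 | 42% v 19% | 37% / 60% | 31% / 50% | 61% / 81% |
| 2.5 | 47% v 18% | 61% / 81% | 49% / 68% | 86% / 96% |
| 3.0 | 51% v 16% | 78% / 91% | 63% / 80% | 95% / 99% |

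Over all three event rates at alpha 0.01, OR up to 2.0 gives 10–42% (75th) and 9–31% (90th). OR 3.0 gives 66–83% at the 75th. With 80 evaluable subjects, power falls by up to about 14 points.

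**4. What the count regression sees.** Eleven solicited items were simulated with the any and moderate-plus-severe rates of protocol Tables 2 and 3 (moderate-to-severe rash assumed 0.5%). The item correlation was 0.3 or 0.5, with 2,000 runs at alpha 0.01.

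- Titer raises severity only (shift 0.2 to 0.5 SD per SD of ln titer): count regression 1% throughout, its type I error. At a shift of 0.3, the 2x2 at the 75th has 28–33% and moderate-to-severe yes/no on ln titer 51–65%.
- Titer raises number and severity (shift 0.3): count regression 79–91%, 2x2 at the 75th 31–34%, yes/no on ln titer 55–66%.

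**The case against.** A reader might infer that a titer-related rise in moderate or severe reactions would usually be missed. The documents do not support that.

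- The plan attaches no test to the 2x2 tables, and alpha 0.01 belongs to the slope alone. Nothing defines a miss, and the powers above describe a test added for comparison.
- Effect sizes and event rates are assumed. Large effects would often show even in the cut table, and at OR 1.5 the continuous model also has little power. Part of the shortfall therefore comes from N = 100 and, at 0.01, the strict alpha.
- If higher titer brings more reactions as well as worse ones, the planned count regression does well, although it would not show that severity was involved. A pure severity effect is an extreme case. In SAP Table B, graded redness and swelling start at 2.5 cm and graded fever at 100.4, so a stronger reaction can also move a subject from Grade 0 to Grade 1 and raise the count.
- The stated question concerns high titers, so an upper-tail split has some logic. The simulations assume a relation linear in ln titer, which favours the continuous model; no threshold effect was tried.
- The protocol's reaction rates cover days 0–14 after one dose with different size grades, so they are only indicative for a 3-day window.
- The titer question is neither an objective nor an endpoint, and severity is summarised in its own right elsewhere.

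These points limit the claim and its weight. They leave standing that the only titer-by-severity analysis has a coarsened predictor and no planned estimate or interval.

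**Conclusion.** The point holds as a structural weakness. Severity is related to titer only through percentile-cut tables with no planned odds ratio, interval or test, and the model using the full titer cannot distinguish grades. The information loss, about 46% at the 75th percentile and 66% at the 90th, needs no assumed effect size, but it does rest on normal ln titer and a linear relation. The power differences (37% or 31% against 61% at OR 2.0 per SD, 25% event rate, alpha 0.01) are illustrations under assumed inputs for a single vaccination. Pooling the five vaccinations would raise power by an amount that depends on within-subject correlation, which the documents do not give. Because the analysis is supportive, the change is worthwhile and cheap, but the primary safety assessment does not depend on it.

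**What to change.** In SAP 9.5, and in the Table 11 shell or a companion table:

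1. Define the outcome by grade: at least one solicited AE of Grade 2 or higher on Table B within 3 days of that vaccination, yes or no.
2. State one titer time point and use it in the linear regression too, for example the last sample before that vaccination. For the first vaccination that is the screening sample. For the fifth it is the Month 12 pre-vaccination sample described in protocol 8.8 or, if none was taken, the latest earlier one.
3. For each vaccination, fit a logistic regression of that outcome on continuous ln titer. Report the odds ratio per doubling, exp(β × ln 2), with a 95% CI. Use Firth penalisation if events are few.
4. For any overall estimate across the five vaccinations, use GEE or a subject-level random effect, because each subject contributes up to five records.
5. Keep the 2x2 tables, labelled as descriptive, and make the text and the Table 11 note agree on the percentile or percentiles shown.

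Cost: SAP wording and one further model per vaccination on data already collected. The downside is one more set of supportive estimates, imprecise at doses with few Grade 2 or higher reactions.
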